This study will include patients age 7 years or older with mutations in *RYR1* (confirmed by previous genetic testing), who are not currently taking antioxidants, and who are able and willing to perform all procedures at the time of enrollment. Children under age 7 may not be

able to successfully follow instructions for outcome measure testing. The accrual ceiling is 100. Withdrawals/dropouts will not be replaced. The target number of completers is 76.

Sixty to 100 age-matched healthy volunteers will be recruited.

NIH employees may participate. The NIH Information Sheet on Staff Research Participation will be provided to any staff member wishing to participate in this study (see Appendix L).

b. Inclusion criteria

Patients:

- Have a confirmed genetic diagnosis of RYR1-related myopathy, including congenital myopathy, OR have a clinical diagnosis of RYR1-related myopathy and a family member with a confirmed genetic diagnosis of RYR1-related myopathy
- Ambulatory.
- 7 years of age or older.
- Preferred: The affected subject has a previous muscle biopsy with available report confirming RYR1-related myopathy histopathology.

Healthy Volunteers:

- Ages 7 and older (15-25 7-12 year olds, 15-25 13-17 year olds, 15-25 18-40 year olds, 15-25 41 and older) without medical condition resulting in or complaints of muscle weakness and/or fatigue.
- The ability to provide consent.

c. Exclusion criteria

Patients:

- Adults who cannot provide their own consent and pediatric participants who do not have a parent able to provide consent
- Patients with a history of liver disease (Liver Function Tests will be collected at baseline and at each study visit as a precautionary measure). Liver disease is defined as moderate to severe hepatic impairment based on the following:
ALT \geq 8x upper limit of normal (ULN) with total bilirubin 2x ULN (plus >35% 'direct' bilirubin) and/or INR >1.5
or
GGT > 2-3x ULN with bilirubin 2x ULN (plus >35% 'direct' bilirubin) and/or INR >1.5
GGT >2-3x ULN and INR >1.5
- Patients with a history of peptic ulcers, gag reflex depression, and esophageal varices. Patients with gastrostomy tubes may be considered for participation, in the case of gag reflex depression or other swallowing or feeding difficulties.

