After data collection at six months, for each individual participant, the participant will immediately begin the second phase of the study when they will be randomized, using block randomization, to a placebo or a study drug group at the end of the 6-month visit to NIH. The allocation scheme is computer-generated using random permuted blocks to maintain balance of the two groups (placebo and control) and to maintain balance between children and adults. The participant will be randomized to the study drug or placebo group by an NIH pharmacist, who is blinded to the allocation scheme. Study drug assignments are recorded by the pharmacist, to be revealed only after the study is complete. BioAdvantex Pharma will provide oral effervescent NAC capsules, (PharmaNac) as well as identically packaged placebo capsules so that participants will not be able to distinguish the treatment from placebo. The study drug group will receive 15mg/kg/day (no more than 1800 mg/day) for the first week. After the first week, subjects who weigh fewer than 50kg will receive 30mg/kg/day of NAC (no more than 2700mg/day) divided TID over a period of six months. To increase compliance, as the tablets are formulated as 900mg each, subjects who weigh greater than 50kg will receive 2700mg/day.

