retest analysis yields a poor correlation ($ICC < 0.40$), then the scales will not be used in the study since they are not primary outcome measures. However, if they yield moderate to high correlation, we will use the scales throughout the entire study.

Randomized, double-blind, placebo controlled, drug trial (Phase 2 of protocol):

Student's t test will be used to compare treatment to control groups. As mentioned in the Introduction, under "Summary", success of the trial will be defined as finding a significant difference in the primary oxidative stress measure of of urine 15-F2t-isoprostane between the treatment and placebo groups at the termination of the study (significantly decreased urine 15-F2t-isoprostane concentration in treatment group compared to placebo group). A sub group analysis will be performed on adults versus children given the difference in dosing. A paired t test will be used to compare subjects to their baseline values. A student's t test will be used to compare the difference in glutathione between 6 months and 12 months, between the two groups. General linear modeling will be used to control for possible confounders such as gender, age, and baseline values. Log transformed values may be used if there is no bell curve. We will use an alpha of 0.05 to determine significance.

We will use the Grounded Theory Method (GTM) of data analysis to analyze the semi-structured interview data. GTM methodically organizes unique individual experiences collected during interviews into comparable categories so that it becomes possible to find commonalities as well as variations in personal experiences. We use GTM because it is particularly effective for analyzing qualitative interview data and because it is rigorous. A GTM approach is appropriate when there is limited knowledge about a substantive area, such as the fatigue and quality of life of individuals with RYR1-related myopathy.

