The primary analysis will be an intent-to-treat (ITT) analysis, i.e. all randomized participants will be included in the analysis. The mechanism for missing data will be evaluated. If missing data are unrelated to the intervention or primary outcome (i.e. missing completely at random or missing at random), the analysis will be based on multiple imputations (20-40 imputed datasets, depending on the extent of the missing data) with a pooled average of the 20-40 imputations included in the final dataset and used in hypothesis-testing analyses. Minimum and maximum value constraints for imputed data will be determined using *per protocol* averages.

Because of uncertainties regarding the true effect size of NAC treatment in our patient population, and the rare nature of this disease possibly limiting accrual, we plan to perform a sample size reevaluation and interim analysis once 30 patients have completed the trial, i.e., when 40% of our potentially achievable accrual reach Month 12.

For the sample size reevaluation, and based on the observed data so far, we will calculate the following: the control group delta and its standard deviation and the standard deviation of the delta for the active arm. Based on these observed parameter values for urine 15-F2t-isoprostane, we will re-calculate the sample size and compare it to the current N=76.

Based on O'Brien-Fleming boundary calculations (O'Brien and Fleming, 1979), the interim analysis will result in one of 3 actions:

1. If there is strong indication of no benefit of NAC in decreasing 15 F2t-isoprostane levels, i.e. if the observed standardized treatment effect is less than -3.36, we will consider stopping the study early for futility.
2. If there is no clear indication of benefit of NAC decreasing 15 F2t-isoprostane levels, i.e. if the observed standardized effect size is between -3.36 and 3.36, we will continue the study and analyze the data at the completion of the study.
3. If there is strong indication that the NAC treatment decreases 15 F2t-isoprostane levels, i.e. if the observed standardized treatment effect is greater than 3.36, we will consider stopping the study early for efficacy.

Stopping the trial early when there is strong evidence for futility or efficacy will reduce patient burden, decrease excess costs, and provide a potential treatment sooner for this rare disease, which currently has no treatment.

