There will be no difference in mean corrected 15-F2t-isoprostane concentration or 6MWT distance, between the *RYR1*-RM and otherwise healthy individuals.

Alternative Hypothesis (H_1)

Corrected 15-F2t-isoprostane concentration will be significantly increased and 6MWT total distance will be significantly decreased in *RYR1*-RM myopathy patients when compared to otherwise healthy individuals.

2. After 30 participants complete their 2nd visit at 6 months (prior to starting study drug/placebo), disease progression will be assessed using paired t-tests to determine changes between 0 and 6-month visits for each outcome measure. For the primary outcome measures (corrected 15-F2t-isoprostane concentration and 6MWT) change between 0 and 6-month time points will be assessed. This analysis will be repeated when all 6-month visits are completed.

Null Hypothesis (H₀)

Corrected 15-F2t-isoprostane concentration and 6MWT total distance will not change significantly between 0 and 6 months in *RYR1*-RM myopathy patients.

Alternative Hypothesis (H₁)

There will be a statistically significant difference between 0 and 6-month values for corrected 15-F2t-isoprostane concentration and/or 6MWT total distance in *RYR1*-RM myopathy patients.

Intervention phase analyses (month 6 to month 12)

- Use an independent t-test (or non-parametric equivalent) to compare pre-intervention (month 6) values for demographics, urine isoprostane and six-minute walk test between NAC versus placebo groups.
- Using multiple imputation (x40 datasets and minimum/maximum value constraints from *per protocol* data) impute missing month 12 data.
- The following GLM should be run both *per protocol* and with ITT datasets.
 1. Run a general linear model comparing month 12 month corrected 15-F2t-isoprostane concentration (corrected_f2-isop_month12, corrected_f2-isop_PGF2alpha_ratio_month12) between NAC and placebo groups controlling for pre-intervention value. Run this model again controlling for established *a priori* confounders including age, sex, height, weight, BMI, smoking status, alcohol status. Variables that do not contribute significantly to the model may be removed. (Exclude RYR023, RYR024, and all healthy volunteers).

Null Hypothesis (H₀)

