There will be a statistically significant and/or clinically meaningful difference between 0 and 6-month graded functional tests (time to completion); Biodex (fatigue indices); Myotools values (grip and pinch strength), MFM (D1, D2, D3 and total % of maximum score), PROMIS (scale scores), FACIT (total score), NeuroQoL (scale scores), MRI (intramuscular fatty infiltration), MFI-20 (total score) in *RYR1*-RM myopathy patients.

3. Additionally, the following will be analyzed:

Optimal measures for fatigability in *RYR1*-RM will be determined using paired t-tests for 6MWT distance and speed, time for graded functional tests, and fatigue index for biodex fatigue test.

Spearman rho correlation, Pearson correlation and/or Bland Altman analysis will also be used to examine the relationship between slow vital capacity and forced vital capacity (L and % predicted). Descriptive statistics and change between baseline and 6 months will be assessed for FVC and SVC (L and % predicted).

Reliability will be assessed for PROMIS, FACIT, MFI, MFM, and NeuroQoL by Cronbach's alpha for internal consistency and by Intraclass correlation coefficient for test-retest.

Intervention phase analyses (intent-to-treat)

- Use an independent t-test (or non-parametric equivalent) to compare baseline values for all secondary outcomes above between NAC versus placebo groups. General linear modeling will be used to control for possible confounders such as such as but not limited to baseline values, gender, age, and baseline values. Log transformed values may be used if there is no bell curve. We will use an alpha of 0.05 to determine significance. Variables that do not contribute to the model may be removed.
- Using multiple imputation (x40 datasets and minimum/maximum value constraints from per protocol data) impute missing month 12 data.
- The following GLM should be run both *per protocol* and with ITT datasets.
- General linear model comparing month 12-month data between NAC and placebo groups (controlling for possible confounders such as but not limited to: baseline value, age, sex, height, weight, BMI, smoking status, alcohol status).

Exploratory Outcome Measures

Aim 1: Anaerobic threshold, NIRS; secreted ER calcium monitoring proteins (SERCAMP) assay in blood and muscle

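### The protocol tests one dataset of averaged imputations and the SAP gives no combining rule, so the primary ITT standard error is too small if arm is imputed on, or the effect is diluted if it is not

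*Protocol*

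**What the plan says.** Protocol Section 10b makes the primary analysis intent-to-treat, with every randomised participant counted. If missingness is judged completely at random or at random, the analysis rests on 20 to 40 imputations, "with a pooled average of the 20-40 imputations included in the final dataset and used in hypothesis-testing analyses". It adds: "Minimum and maximum value constraints for imputed data will be determined using *per protocol* averages".

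The SAP, under the intervention-phase analyses of the primary outcomes, says: "Using multiple imputation (x40 datasets and minimum/maximum value constraints from *per protocol* data) impute missing month 12 data". It continues: "The following GLM should be run both *per protocol* and with ITT datasets". The model compares month-12 values between arms and adjusts for the pre-intervention value. The same imputation instruction is repeated for the secondary outcomes.

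Neither SAP section says how results from the 40 datasets are to be combined, and neither document lists the variables in the imputation model. For the Phase 2 comparison, Protocol Section 10a first names a simpler test: "Student's t test will be used to compare treatment to control groups". It then adds general linear modelling to control for confounders.

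**The concern.** Multiple imputation gives valid inference because each completed dataset is analysed separately. The spread between datasets is then added to the variance. The protocol reverses the order: it averages first and tests once. The average of 20 to 40 imputed values is close to a regression prediction. It has almost no residual scatter, and the between-imputation variance is gone. The test nevertheless treats it as an observed value.

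The consequence depends on an unstated choice. With arm in the imputation model, the treatment estimate is about right but its standard error is too small. With arm left out, imputed values carry no treatment difference and the estimate is pulled toward zero. Because trial success is defined by a significant isoprostane difference at 0.05 (Sections 1 and 10a), this bears on the decisive p-value and its confidence interval.

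Two related points leave the ITT dataset undefined:

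- **Bounds.** They come from per-protocol averages in the protocol and from per-protocol data in the SAP. A mean is not a minimum or a maximum.
- **Withdrawals.** Section 4d (Pill count) withdraws participants found non-compliant on returning for the third visit, which is when outcomes are measured. Section 10b counts everyone randomised. Nothing says whether month-12 values already collected from those participants are kept or imputed.

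**Working it through.** **Inputs from the documents.** Two-sided alpha is 0.05 (10a, 10b) and allocation is 50:50 (front matter). For 3a, with an accrual ceiling of 100: "The target number of completers is 76". On timing, 4a says of participants: "they will be randomized, using block randomization, to a placebo or a study drug group at the end of the 6-month visit to NIH".

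**The plan's own figures.** The glutathione planning values (difference 1.7, SDs 2.34 and 2.80, Satterthwaite t test) give 79.8% power at 37 per group and 80.9% at 38, so the stated 38 reproduces. Planned loss is (100 - 76)/100 = 24%. Section 10b's wording of 76 and 24 per group with a ceiling of 200 conflicts with 3a on totals but gives the same 24%.

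**Assumed share imputed, m.** The documents give no month-12 missing count. The 24% includes losses in the six months before randomisation, so I use m = 6%, 12% and 24%, with 24% as the upper planning figure.

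**Formula, arm in the imputation model.** With n patients per arm and residual variance σ²:

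- Only the observed n(1 - m) values contribute residual scatter, but n are counted. The reported variance is proportional to σ²(1 - m)/n.
- The information really comes from n(1 - m) values. The true variance is proportional to σ²/[n(1 - m)].
- Reported SE / true SE = 1 - m, so type I error = 2 × [1 - Φ(1.96 × (1 - m))].
- m = 0.06: 1.96 × 0.94 = 1.842, giving 6.5%. m = 0.12: 1.96 × 0.88 = 1.725, giving 8.5%. m = 0.24: 1.96 × 0.76 = 1.490, giving 13.6%.

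**Formula, arm omitted.** The estimate shrinks by about (1 - m). Its true variance becomes (1 - m)² × σ²/[n(1 - m)] = σ²(1 - m)/n, which matches the reported variance. Alpha therefore holds, but a true 0.60 SD becomes 0.60 × 0.94 = 0.56, 0.60 × 0.88 = 0.53 and 0.60 × 0.76 = 0.46.

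**Simulation.** Assumptions: 50 per arm, normal outcome, correlation 0.5 with the pre-intervention value, missingness mildly dependent on that value, 40 proper imputations and a baseline-adjusted model. There were 5,000 null runs (Monte Carlo error at most 0.5 points) and 2,000 runs with a true effect of 0.60 SD.

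| Missing | Type I, averaged, arm in | Type I, Rubin, arm in | SE, averaged / Rubin | Type I, averaged, arm out | Estimate of 0.60, arm in | Estimate of 0.60, arm out |
|---|---|---|---|---|---|---|
| 6% | 6.9% | 5.2% | 0.94 | 5.2% | 0.60 | 0.56 |
| 12% | 8.5% | 4.7% | 0.88 | 5.0% | 0.59 | 0.53 |
| 24% | 14.6% | 5.2% | 0.75 | 4.4% | 0.59 | 0.45 |

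**Sensitivity** (averaged dataset, arm in, type I error at 6 / 12 / 24% missing):

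- Second simulation, missing completely at random, 38 and 50 per arm: 6.7-7.1% / 8.3-8.8% / 13.6-13.9%.
- The same, with imputations clipped to the observed minimum and maximum: 6.1-6.3% / 7.6-8.7% / 13.7-13.8%.
- The same, 50 per arm, correlation 0 or 0.8: 6.1-6.2% / 8.5-9.4% / 13.7-14.1%.
- First simulation with 19 per arm: 6.4% / 8.9% / 14.3%. A smaller trial is not protected.
- Unadjusted t test, correlation 0.5: 6.0-6.5% / 7.2-7.5% / 10.9-11.5%. With correlation 0.8: 5.7% / 6.8% / 8.1%.

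**The case against.** The strongest reply is that the SAP does not repeat the averaging. Asking for 40 datasets and a model run on ITT datasets is compatible with analysing each one and pooling, and with arm included that gives 4.7-5.2%. The SAP's fault is silence rather than a wrong method, and an analyst might do the right thing. That stands as far as it goes. But the protocol's averaging sentence is then the only combining instruction in either document, and it describes values placed in a dataset before testing. Under Rubin's rules a pooled quantity is a result and never enters a dataset.

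Four further points affect size:

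- **The protocol's rule is conditional** on missingness being judged ignorable. True, but no alternative is described, and the SAP imputes without that condition.
- **Inflation is smaller for the unadjusted t test.** True, as shown above. The headline figures belong to the SAP's baseline-adjusted model.
- **The missing share is unknown.** True. At 6% the excess is only one to two points. Nor is 24% a strict bound if values from visit-3 withdrawals are discarded.
- **Rubin's rules are not the only valid remedy.** True. Complete-case analysis with baseline adjustment held alpha in the same simulation (5.2%, 4.9%, 5.1%). But the plan commits to an analysis of all randomised patients by multiple imputation, and the fix keeps that commitment.

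The bounds and the withdrawal rule add nothing to the main error rates. They need reconciling on their own account.

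**Conclusion.** The concern holds. As written in the protocol, the primary ITT test treats averaged imputations as data, and nothing in the SAP replaces that rule. Under the SAP's baseline-adjusted model with arm in the imputation model, the true type I error is about 6-7%, 8-9% and 13-15% at 6%, 12% and 24% missing, against a nominal 5%. With arm omitted, type I error stays near 5% but the effect shrinks by about the share imputed. A reader of the two documents cannot tell which would apply.

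The figures assume normal outcomes and missingness that is completely at random or depends only on the pre-intervention value. The 6% and 12% shares are assumptions, and 24% is the whole-study planning loss. The mechanism depends on none of these; the size scales with the share actually imputed. This must be fixed because it affects the test that defines success.

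**What to change.** 1. In Protocol Section 10b and both SAP intervention-phase sections, replace the averaging rule with wording to this effect: each of the 40 imputed datasets is analysed with the primary general linear model; estimates and standard errors are combined by Rubin's rules; the imputation model includes treatment arm and the pre-intervention value. Both parts are needed. With arm omitted, Rubin's rules still give 0.45 for a true 0.60 at 24% missing, and reject only 0.8% of the time under the null.
2. Give one definition of the imputation bounds in all three places and state how the minimum and maximum are calculated.
3. Reconcile the pill-count withdrawal rule with the ITT definition: state that month-12 values already observed stay in the ITT analysis and that these participants leave only the per-protocol set.
4. Report, by arm, how many randomised patients have imputed month-12 values.

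The cost is document wording and a few lines of code, with no new data. Where the averaged dataset would have understated the standard error, confidence intervals will be wider and p-values less favourable.

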Hypothesis: 15-F2t-isoprostane will be significantly increased in RYR1-RM myopathy patients compared to healthy individuals.

Hypothesis: 6MWT distance will be significantly decreased in RYR1-RM patients compared to healthy individuals.

- 2) After 30 participants complete their 2nd visit at 6 months (prior to starting study drug/placebo), disease progression will be assessed using paired t-tests to determine changes between 0 and 6 month visits for each outcome measure. For the primary outcome measures, 15-F2t-isoprostane and 6MWT will be assessed for change between 0 and 6 months. This analysis will be repeated when all 6 month visits are completed.

Hypothesis: 15-F2t-isoprostane concentration will not change significantly between 0 and 6 months in RYR1-RM myopathy patients.

Hypothesis: 6MWT distance will not change significantly between 0 and 6 months in RYR1-RM patients.

The purpose of the above interim look analyses (under #1) is to confirm that the affected subjects are different from healthy individuals. Because of the rolling nature of the study and the length of time involved to complete the first phase of the study, this allows evaluate whether these outcomes are different from healthy individuals, as expected, in order to confidently proceed with the study. The purpose of the above interim look analysis (under #2) is to characterize the natural history and variability of the RYR1-RM patients for these specific outcome measures and to contribute novel data to the field of RYR1 as soon as possible for future trial design, given that an N of 30 is a large number in rare disease.

Optimal measures for fatigability in RYR1-RM will be determined using paired t-tests for 6MWT distance and speed, time for graded functional tests, and fatigue index for biodex fatigue test. Correlative analysis (Pearson correlation and/or Spearman rho) will be used to examine the linear relationship between subjective fatigue measures (FACIT and MFI) and the salivary fatigue biomarker to the objective fatigability measures mentioned above as well as to compare forced vital capacity to slow vital capacity. Spearman rho correlation, Pearson correlation and or Bland Altman analysis will also be used to examine the relationship between slow vital capacity and forced vital capacity.

Reliability will be assessed for PROMIS, FACIT, MFI, MFM, and NeuroQoL by Cronbach's alpha for internal consistency and by Intraclass correlation coefficient for test-retest. If the test-

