The primary outcome measure is being changed, initially due to pipette calibration error in the lab at NIH. Additional review of our data at Emory after sending a second batch of samples and

further literature review identified further justification for changing the primary oxidative stress biomarker from glutathione (GSH) to 15-Ft2-isoprostane:

- The processing of GSH and its oxidized form GSSG often results in methodological artifacts. For instance, sample acidification for protein precipitation leads to an increase in GSSG levels thus decreasing GSH:GSSG ratio (Marrocco et al. 2017). The assay is sensitive to exposure to air/time and sample volume and is therefore prone to error. The aforementioned methodological artifacts are not unique to this protocol and have been described previously (McGill et al. 2015).
- During the current protocol, such methodological issues arose at Emory in addition to the pipette calibration issue at NIH. For example, when the second sample for each patient was rerun at Emory, including samples unaffected by the pipette error, the results between the first patient and second patient sample were unreliable. These methodological errors in GSH as a biomarker and the recurrent, significant time delays for processing by Emory, in addition to the pipette error, prompted a change in primary outcome measure from GSH to 15-Ft2-isoprostane.
- 15-Ft2-isoprostane was collected on each individual at each visit as a secondary outcome measure for oxidative stress throughout the life of the protocol. The change from GSH to 15-Ft2-isoprostane is being made prior to treatment allocation un-blinding and prior to statistical analyses, which is the optimal time to change a primary endpoint when such a change is required (Evans, 2007). Changes in primary endpoints are reported in approximately 30% of clinical trials (Ramagopalan, 2014).

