- Elevated oxidative stress is a hallmark pathological feature in RYR1-RM and has been identified in several pre-clinical models of the disease (Durham et al. 2008, Dowling et al. 2012, Lee et al. 2017, Michelucci et al., 2017). In particular, lipid peroxidation of mitochondrial membranes has been implicated as a central pathomechanism that leads to severe mitochondrial dysfunction and/or death in the RYR1Y522S/W mouse model (Durham et al. 2008). Notably, treatment of the aforementioned mice with N-acetylcysteine (NAC), (ad lib via drinking water for 8 weeks) rescued lipid peroxidation and concomitantly prevented previously observed decrements in force generation (Durham et al., 2008). These findings have recently been supported by a longer-term study of NAC treatment in the same mouse model in which NAC treatment led to a decreased number of structural cores and improved skeletal muscle function (Michelucci et al., 2017).
- 15-F2t-isoprostane has been reported as the most reliable in vivo biomarker of oxidative stress and is a measure of lipid peroxidation (Milne et al. 2007, van 't Erve et al., 2017). Moreover, a typical 15-F2t-isoprostane concentration has been established through substantial data collection from otherwise healthy volunteers (n= 1881) allowing comparisons to be made to disease populations (van 't Erve et al., 2017). Finally, when our participants' baseline and 6 month (untreated) isoprostane levels were compared, the findings were not significantly different, suggesting reliability of this biomarker in our population, in contrast to our GSH data analysis of the same time points.

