Anaerobic threshold using NIRS will be evaluated for patterns in individuals with *RYR1*-RM compared to healthy controls. From this evaluation, the tissue saturation index will be calculated as $TOI = [O_2-Hb] / Tot-Hb$. The rate of decline and rise in TOI will be compared to healthy controls. NIRS data will also be obtained during CPET and Biodex

testing and may be used to generate new hypotheses regarding oxidative metabolism in *RYR1*-RM.

SERcaMP levels will be tested in an exploratory fashion in patient-derived myotubes to assess whether Ca^{++} levels are normal in the sarcoplasm and/or cytosol. This will generate new hypotheses regarding Ca^{++} dysregulation in *RYR1*-RM.

Aim 2: CPET, EIM, salivary FBI, melatonin, cortisol and DHEA; QoL qualitative interview

Correlative analysis (Pearson correlation and/or Spearman rho) will be used to examine the linear relationship between subjective fatigue measures (FACIT and MFI) and the salivary biomarkers (FBI, melatonin, cortisol, DHEA) to the objective fatigability measures mentioned above, such as CPET. This data may be used to generate new hypotheses fatigue and fatigability in *RYR1*-RM.

The QoL interviews will be mined for common themes across participants. Interviews will also be mined for any comments about differences in QoL before and after treatment. This data may be used to generate new hypotheses regarding QoL in individuals with *RYR1*-RM.

All data may be used for additional exploratory analyses, particularly for the natural history phase of the study. These additional analyses which will not include or alter 12-month data/results of the intervention phase analysis. This is due to the rare nature of this disease and thus the substantial value of this data to contribute findings in this population.

[name], PNP-BC
NIH/NINR/TIB NIH/NINR/TIB
[name]
[name]
[name]
[contact]
E-mail: [contact]

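### A non-significant month 0 to 6 change is read as biomarker reliability, and paired t-tests are named as the way to pick the best fatigability measures; a test of mean change can do neither

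*Protocol*

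**What the plan says.** **Biomarker.** Protocol section 10.b lists the reasons for replacing glutathione (GSH) with urine 15-F2t-isoprostane. One is that, when untreated baseline and 6-month levels were compared, "the findings were not significantly different, suggesting reliability of this biomarker in our population". The same sentence sets this against the GSH data at those time points. It gives no test, sample size, mean change, SD or interval. The test planned for month 0 to 6 change, in Protocol 10.a and in the SAP's natural history analyses, is a paired t-test.

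**Fatigability measures.** Protocol 10.a states: "Optimal measures for fatigability in RYR1-RM will be determined using paired t-tests for 6MWT distance and speed", and goes on to the graded functional tests and the Biodex fatigue index. The SAP (Secondary Outcome Measures, Natural History Phase, Aim 2, item 3) repeats that these measures "will be determined using paired t-tests for 6MWT distance and speed, time for graded functional tests". Neither document says what result would make a measure optimal.

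**What is planned elsewhere.** The same parts of both documents assign Cronbach's alpha and a test-retest ICC to PROMIS, FACIT, MFI, MFM and NeuroQoL. For scales with an ICC below 0.40 the Protocol adds: "then the scales will not be used in the study since they are not primary outcome measures". No ICC or within-patient SD is planned for isoprostane, the 6-minute walk test (6MWT), the timed tests or Biodex, although Protocol 4.a names the Biodex fatigue index among the measures to be validated.

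**The concern.** Reliability is about individuals: does a patient with a high value at month 0 still have one at month 6, and how large is the within-patient scatter? A paired t-test is about the group mean. Large within-patient scatter widens the standard error and makes non-significance more likely, so reading non-significance as reliability can reward the noisier marker. By the same logic, a significant GSH change would not by itself show GSH to be unreliable.

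The fatigability rule has the same flaw and a second one: with no criterion stated, a p-value cannot rank the measures.

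At stake is what the natural history phase can conclude. One stated purpose of its 6-month look is to "characterize the natural history and variability of the RYR1-RM patients for these specific outcome measures", as an aid to future trial design. An unsupported reliability claim, or an arbitrary choice of best measure, would carry into later trials in a rare disease.

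**Working it through.** The documents give no figure behind the reliability statement, so there is nothing to reproduce. The check is how the rule *non-significant means reliable* behaves.

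**Inputs.** From the documents: two-sided alpha 0.05 (Protocol 10.b gives the sidedness, for the sample size); n = 30, the size of the 6-month look in Protocol 10.a; n = 76, the target number of completers in Protocol section 3, as a larger case. Assumed: a paired t-test, equal SDs at the two visits, month 0 to 6 correlation r, and a true mean shift d in units of the SD across patients at one visit.

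**Formula.** The SD of the paired difference is √(2(1−r)), so the noncentrality is d/√(2(1−r)) × √n. The probability of a non-significant result is the noncentral-t probability between the two critical values.

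Example, n = 30, d = 0.2 (critical value 2.045):
- r = 0.39: 0.2/√1.22 × √30 = 0.992, non-significant in 84.0%.
- r = 0.9: 0.2/√0.2 × √30 = 2.449, non-significant in 34.2%.

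| n | r | d = 0 | d = 0.1 | d = 0.2 | d = 0.3 |
|---|---|---|---|---|---|
| 30 | 0.39 | 95% | 92% | 84% | 70% |
| 30 | 0.9 | 95% | 78% | 34% | 6% |
| 76 | 0.39 | 95% | 88% | 66% | 35% |

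With no shift the answer is 95% at every r, including r = 0, so the result says nothing about reliability. With a shift the rule runs backwards. The value 0.39 simply stands for a weakly reproducible marker.

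**Stability of the mean.** At n = 30 the shift detectable with 80% power is about 0.58 SD at r = 0.4 and 0.24 SD at r = 0.9. Non-significance therefore does not establish an unchanged mean either.

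**Ranking two measures.** Simulated independent measures, n = 30, r = 0.9 against r = 0.6:
- No shift: the more reproducible measure has the larger p-value in 50% of samples, which is chance.
- Shift of 0.2 SD in both: it has the smaller p-value in 80% and the larger in 20%, so choosing by smallest or by largest p picks opposite measures.
- The sample ICC orders the pair correctly in more than 99% in both cases, and in 94% for r = 0.8 against 0.6 with no shift.

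Equal p-values can also hide unequal measures. With r = 0.9 and d = 0.2, or r = 0.6 and d = 0.4, the noncentrality is 2.449 in both (0.4/√0.8 × √30), and both are significant in 66% of samples. The within-patient SDs, √(1−r), are 0.32 and 0.63.

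**Limits of the alternative.** At n = 30 an observed ICC of 0.60 has a 95% CI of 0.32 to 0.79 (one-way, exact F). Judging measures by whether separate CIs overlap would leave r = 0.9 and 0.6 undistinguished in 44% of samples with no shift, and r = 0.8 and 0.6 in 89%.

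**The case against.** **The wording is cautious and is one argument among several.** The Protocol says only that the result suggests reliability. It also relies on published work, stating that "15-F2t-isoprostane has been reported as the most reliable in vivo biomarker of oxidative stress", and on GSH assay failures, including that on rerun "the results between the first patient and second patient sample were unreliable". All of that stands. A reader might infer that the endpoint switch is unsupported, or that isoprostane is unreliable in this population. The documents support neither: the switch has other grounds, and no within-patient figure is given in either direction. The caution does not rescue the clause, because the test result does not bear on reliability even weakly.

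**Paired t-tests are not the only evidence planned.** Protocol 10.a also plans correlations of the fatigability measures with FACIT, MFI and the salivary biomarker, and it expects 6MWT not to change. This is fair, but neither is named as the selection rule.

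**Optimal need not mean most reproducible.** It could mean stable, responsive or related to fatigue, and this stands. ICC also rises with the spread between patients, and this cohort runs from age 7 upward, so a high ICC may partly reflect age or body size. The defect is that the named test cannot rank measures on reproducibility and no other criterion is given. It is not that ICC was the only right choice.

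**The 0.40 cut-off does not transfer.** It was set for questionnaire scales, retested at one month. A reader might hold isoprostane or 6MWT to it over six months; the documents give no basis for that.

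**A paired test is useful for drift.** Agreed; mean change should still be reported, with an interval.

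**Conclusion.** Wrong as written, and minor. The step from a non-significant month 0 to 6 difference to reliability is invalid whatever test and sample size lay behind it. The percentages are illustrations that rest on a paired t-test, equal SDs and assumed correlations and shifts; none is an estimate for this trial. Selection of optimal fatigability measures by paired t-test fails for the same reason, and because no criterion is stated.

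The effect is confined to natural history conclusions: what may be said about isoprostane reproducibility in these patients, and which fatigability measure is put forward as best. The outcome list in Protocol section 9 and the randomised month 12 comparison, including its type I error, are not touched.

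**What to change.** 1. **Protocol 10.b.** Delete the reliability clause, or replace it with the month 0 to 6 isoprostane ICC (absolute agreement) with 95% CI and the within-patient SD, or CV if analysed on the log scale. Note that six months mixes true change with measurement error, so a low value alone would not prove the assay unreliable.
2. **Protocol 10.a and SAP Aim 2 item 3.** State what optimal means. In place of selection by p-value, report for 6MWT, the timed tests and the Biodex fatigue index the month 0 to 6 ICC with 95% CI, the within-patient SD beside it, and the mean change with 95% CI. Read these with the correlations already planned. Treat 6MWT distance and speed as one measure, since speed is calculated from the same walk. If two measures are formally compared, use a paired method such as a bootstrap over patients, not overlap of separate CIs. Do not apply the questionnaire cut-off of 0.40.
3. **Both documents.** Do not claim stability from p ≥ 0.05 alone; give the CI for the month 0 to 6 change.

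**Cost.** A little extra analysis of data already collected. The within-patient SD is the SD of the paired differences divided by √2, and the planned t-test already produces that SD. The SAP leaves room for the work: "All data may be used for additional exploratory analyses, particularly for the natural history phase of the study". The price is a reliability figure that may be less favourable than the present wording and, near n = 30, imprecise.
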